### 9.3 Insertion property analysis

From an isotropic voxel set (i.e. DICOM data) with the Ramos et al. algorithm to extract radiological parameters automatically from CT/DVT images and via surgical questionnaire the following parameters will be collected: Insertion related events (Tip-foldover, Scala displacement, Electrode extrusion/shallow-insertion, Over-insertion), Homogeneity Factor and Modiolar Proximity

For the exploration of the candidate algorithm insertions that have insertion related events or a poor medial lateral should be excluded from the dataset. These insertions should still be included in the database, with the appropriate classification.

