## 8 Design of the clinical investigation

### 8.1 General

The current clinical investigation is designed as descriptive research with sequential enrolment. The treatment schedule is according to the clinical routine visit schedule by prospectively adding a one minute trans-impedance and voltage measurement to the clinical routine measurements. The purpose of the clinical investigation is to collect and describe the characteristics of the trans-impedance and voltage measurements to explore the specificity of a candidate algorithm that has been developed to detect certain anomalous electrode array positions. Insertions will be classified based on the electrode position in relation to the cochlea structures as determined from pre- and post-operative CT scans. The classification will establish an insertion as either normal or showing one or more anomalous properties. The study will then provide the candidate algorithm with the 154 classified insertions to explore the specificity of the algorithm, this should allow a specificity of up to 98% to be established with a 90% confidence. The trans-impedance and voltage measurements are obtained at repeated visits to evaluate the candidate algorithm specificity over time.

 Assuming up to 9 anomalous insertions in the sample of 154 implantations.

Blinding procedures are not appropriate for the voltage and trans-impedance measures to be collected with the clinical routine software CSEP, as it is not possible to conceal the presence, or absence, of the devices from the investigators.

Since the candidate algorithm to detect certain anomalous electrode array positions has not been implemented in any CE marked and TGA approved software, no real time feedback on any insertion related events will be provided to the clinician nor surgeon throughout the surgery nor aftercare. The surgeon and the clinician shall not deviate from their established clinical routine measures as CT imaging, x-ray or objective measures to detect anomalous electrode array positions and are advised not to interpret the voltage and trans-impedance measures.

In addition, the data will be analysed to establish the normative range of trans-impedance and voltage measurements in CI532 and CI512 electrode arrays, the correlation to NRT measurement, to correlation to electrode-to-modiolus distance (from CT/DVT Scans) and the normal variations of those measures over time.

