The CT/DVT imaging before and after surgery and the CSEP measurements during and after surgery is part of the clinical routine in CI treatment and patients will be selected who follow this clinical routine.

In addition, the measurements, CT/DVT scans and classifications will be de-identified and stored in a database to support the further development and validation of algorithms. Those insertions showing the presence of anomalous properties will be excluded from the dataset that is presented to the candidate algorithm but will be included in this database. To allow for the exclusion of these insertions an additional 9 subjects are added to the study.

Depending on the recommended practice in the clinics the measures of surgeries performed by experienced and unexperienced surgeons will be collected. For retracement the name of the inserting surgeon is labelled on the surgical questionnaire.

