### 8.3.7 Number of subjects required to be included in the clinical investigation

154, assuming that 9 recipients will not be suitable for the evaluation of the algorithm due to the occurrence of an insertion anomaly.

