## 9 Statistical Considerations

### 9.1 Sample Size Calculation

An in-depth description of the statistical characterisation and correlation will be part of the Statistical Analysis Plan. Final statistical analysis will be conducted on a clean and complete database after database closure.

The candidate algorithm provides the ability to detect gross electrode position anomalies (eg. tip fold-over or electrode not in the cochlea). It provides binary outputs; a value of zero (negative result) or a value of one (positive result). A value of zero indicates that the algorithm concluded that an anomalous position has not occurred and the value of one indicates that the algorithm concluded that an anomalous position has occurred. To be useful as a tool that can replace routine use of X-rays and CT scans, the algorithm is required to have a minimal false positive rate. To ensure that this expectation is reasonably fulfilled, the 98% specificity target is set to be the lower bound of the 90% binomial confidence interval for the specificity of the algorithm. An iterative approach was adopted to estimate the required patient sample size which takes into account the likelihood of anomalous position events. It was assumed that the occurrence of a tip fold-over (the principal form of position anomaly under consideration) follows a binomial distribution with a positive probability of around 4% based on the weighted average percentage for tip fold-overs in pre-curved arrays reported by Grolman et al. 2009 and Zuniga et al. 2016. Using the Clopper-Pearson method a sample size of 154 was selected, which gives an 89% chance of 9 or less tip fold-overs taking place, resulting in at least 145 'normal' insertions. If the algorithm correctly diagnoses all 145 insertions, the lower bound of the two-tailed 90% confidence interval for specificity will be 97.97% which is approximately 98%. In other words, if the algorithm correctly identifies all 145 cases as 'normal' then it can be concluded that its specificity is 98% or better with 90% confidence.

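### The 89% chance of at least 145 normal insertions allows for tip fold-overs only, although the Protocol also excludes other insertion anomalies

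*Protocol*

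**What the plan says.** **Derivation of the allowance.** Protocol 9.1 takes a fold-over probability of about 4% and selects 154 implantations, "which gives an 89% chance of 9 or less tip fold-overs taking place", leaving at least 145 normal insertions. SAP 2.2 does the same with p = 0.04139. Appendix A builds that rate from two series of fold-over counts in perimodiolar arrays. Both documents say that fold-over is taken as the main form of anomaly; neither gives a rate for any other.

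**How the allowance is described elsewhere.** Protocol 8.3.7 gives the number of subjects as "154, assuming that 9 recipients will not be suitable for the evaluation of the algorithm due to the occurrence of an insertion anomaly". Footnote 4 to Protocol 8.1 reads "Assuming up to 9 anomalous insertions in the sample of 154 implantations". SAP 3.1 attaches the 89% to having at least 145 patients with normal insertions.

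**What is excluded.** Protocol 9.3 collects "Insertion related events (Tip-foldover, Scala displacement, Electrode extrusion/shallow-insertion, Over-insertion), Homogeneity Factor and Modiolar Proximity" and then states: "For the exploration of the candidate algorithm insertions that have insertion related events or a poor medial lateral should be excluded from the dataset". Protocol 8.1 says: "Those insertions showing the presence of anomalous properties will be excluded from the dataset that is presented to the candidate algorithm", and adds: "To allow for the exclusion of these insertions an additional 9 subjects are added to the study". Protocol 9.2 likewise confines the specificity data to insertions with no anomalous position on CT.

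**Related passages.** Protocol 8.1 also says: "The study will then provide the candidate algorithm with the 154 classified insertions to explore the specificity of the algorithm". SAP 6 leaves confirmed anomalous positions out of the analysis without naming which analysis. SAP 3.3 states its own exclusion for secondary objective 2; SAP 3.2 is silent for secondary objective 1. SAP 2.2 calculates a positive predictive value (PPV) of 66.02% with fold-over as the condition. Protocol 3 defines PPV for any anomalous position and sets an aim of 60%.

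**The concern.** The probability and the exclusion rule describe different events. The probability concerns ten or more fold-overs. The rule removes fold-overs and also every other listed event and poor medial-lateral positions. Calling fold-over the principal anomaly justifies making it the leading term; it does not set the other terms to zero.

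What is at stake is the meaning of a stated planning assurance. Someone reading SAP 3.1 would take 89% as the chance that the specificity analysis has its 145 insertions. The figure is steep in the exclusion rate, so a few further exclusions change it a good deal.

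The PPV raises a smaller question of the same kind: the condition behind the 66% is not the condition in the definition that goes with the 60% aim.

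**Working it through.** **Inputs.** N = 154 and an allowance of 9 (Protocol 9.1, SAP 2.2). Fold-over counts of 5 in 0.48 × 303 arrays and 4 in 72 arrays (Appendix A). Two-sided 90% interval, so 5% in each tail (SAP 2.1).

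**Step 1: reproduce the plan's figure.**
p = (5 + 4) / (0.48 × 303 + 72) = 9 / 217.44 = 0.04139.
P(X ≤ 9), with X binomial (154, 0.04139), is 0.892. This is the stated 89%, and it is correct for fold-overs.

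**Step 2: apply the full exclusion rule.** Let q be the total proportion excluded. At least 145 normal insertions means X ≤ 9 with X binomial (154, q). The documents give no q, so the totals below 4.14% in this table are assumptions.

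| Total exclusion rate q | Expected exclusions beyond fold-overs, 154 × (q − 0.04139) | P(at least 145 normal) |
|---|---|---|
| 4.14% (fold-over only) | 0 | 0.892 |
| 5% | 1.3 | 0.757 |
| 6% | 2.9 | 0.555 |
| 8% | 5.9 | 0.204 |

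The probability falls to 80% at q = 4.8% and to 50% at q = 6.3%. At q = 6% the expected number of normal insertions is 154 × 0.94 = 144.8.

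**Step 3: effect on precision.** With all n insertions classified correctly, the exact lower bound is 0.05^(1/n). This is 0.97955 for n = 145 and 0.97898 for n = 141, a loss of about 0.06 percentage points for four fewer insertions.

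**Step 4: PPV.** SAP Equation 5 gives 0.0414 × 0.90 / (0.0414 × 0.90 + 0.9586 × 0.02) = 0.03726 / 0.05643 = 0.660, as stated. Insertions with other anomalies sit inside the 0.9586, yet specificity is measured only in insertions free of every anomaly.

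To see the sensitivity, assume that such insertions are a share f = 4% of the total and that a proportion r of them is flagged. All flags are then D = 0.03726 + (0.9586 − 0.04) × 0.02 + 0.04 × r. Correct flags are 0.03726 if only fold-over counts, or 0.03726 + 0.04 × r if any anomaly counts.

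| r (assumed) | D | PPV, fold-over only | PPV, any anomaly |
|---|---|---|---|
| 0 | 0.05563 | 67% | 67% |
| 10% | 0.05963 | 62% | 69% |
| 20% | 0.06363 | 59% | 71% |

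The direction of the shift from 66% depends on the definition. Both f and r are invented for illustration.

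**Step 5: passages side by side.** Protocol 8.1 first gives the algorithm all 154 insertions and later in the same section withholds the anomalous ones; Protocol 9.2 and 9.3 agree with the withholding. Read literally, SAP 6 also removes anomalous positions from the association with electrode position in SAP 3.2, which does not mention any exclusion.

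**The case against.** - **The simplification is disclosed.** Protocol 9.1 and SAP 2.2 attach the 89% to fold-overs by name. This stands for those sentences. What remains is the step from there to 145 normal insertions, and SAP 3.1, which makes that step without the qualification. Neither 89% nor 145 appears in Protocol 8.3.7 or footnote 4; only the allowance of 9 does, as an assumption.
- **89% need not be an upper limit.** Protocol 8.4.2 provides for correction during surgery with measurements repeated afterwards. A corrected fold-over might end as a normal insertion and raise the count. The documents do not say how such cases are classified, so the upper-limit statement carries that condition.
- **The size is assumed.** This stands. Protocol 3 speaks of a few percent for the anomalous modalities. If that is a combined rate, 4.14% may be close to the total and 8% lies above it; only a per-modality reading makes 8% plausible. Poor medial-lateral position has no cut-off, so its frequency cannot be inferred.
- **Little follows for the result.** This also stands: Step 3 shows a trivial loss, and the study is described as exploratory.

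Three stronger readings are tempting, and the documents do not support them. One is that the study is too small and needs more patients; without a total rate and with so little effect on the bound, that does not follow. (Even 145 of 145 falls just short of 98%, which needs 149 of 149, but that is a separate matter.) Another is that the PPV calculation is wrong or has no target: SAP 2.2 uses fold-over throughout, its arithmetic is right, and PPV is not an endpoint. The third is that algorithm output must be produced for the excluded insertions: the Protocol deliberately withholds them, so such a table would be an optional addition.

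**Conclusion.** The point holds as a misstated planning probability. The 89% is right for nine or fewer fold-overs but is not the chance of at least 145 normal insertions under Protocol 8.1, 9.2 and 9.3. Unless corrected insertions count as normal, it is an upper limit, reached only if every other listed exclusion has zero incidence. Under assumed total rates of 5%, 6% and 8% the chance would be 76%, 55% and 20%; these show sensitivity and are not estimates. The consequence for the precision of specificity is negligible.

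The PPV point is secondary. The 66% is a valid fold-over-only planning figure, but it is not directly comparable with a 60% aim tied to the broader definition in Protocol 3. The statement that all 154 insertions go to the algorithm is loose wording that the later passages largely settle. The scope of SAP 6 for secondary objective 1 is open and should be stated.

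**What to change.** 1. In SAP 3.1, and at the step to 145 normal insertions in Protocol 9.1 and SAP 2.2, state that the 89% allows for tip fold-overs only. Alternatively, give the probability over a stated range of total exclusion rates.
2. In Protocol 8.3.7 and footnote 4, state that the allowance of 9 was derived from tip fold-overs only.
3. In SAP 2.2 and Protocol 9.1, label the 66% (over 60% in the Protocol) as a fold-over-only planning figure, or align the definitions of prevalence, specificity and PPV before comparing it with the 60% aim.
4. In Protocol 8.1, reconcile the sentence that gives all 154 insertions to the algorithm with the withholding rule there and in 9.2 and 9.3.
5. Reconcile SAP 6 with SAP 3.2, stating whether anomalous positions enter the association with electrode position.
6. Optional: tabulate algorithm output in the excluded insertions by anomaly type, as a supplement outside the primary specificity. This would relax the withholding rule and rest on few cases.

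Items 1 to 5 are wording changes to the Protocol and SAP, with no new patients, measurements or scans. The price is that the stated assurance may read lower than 89%.

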The candidate algorithm is provided with the trans-impedance measurements and indicates whether a tip fold-over or array outside the cochlea have been detected. For the feedback from this algorithm to be clinically useful it must be shown that the specificity is sufficiently high to ensure that the surgeon is not unnecessarily prompted to take action (confirmation of electrode position by imaging) when not required. Current methods for detecting anomalous electrode position without relying on imaging either use manually-perceived force feedback from the electrode array (Dirr et al. 2013, Pile et al. 2013) or measurement of neural activity, (Grolman et al. 2008, Zuniga et al. 2016). Dirr et al. shows a positive predictive value of 29% using the sense of increased physical resistance during insertion whereas Grolman did not comment on the positive predictive value of the spread of excitation technique and Zuniga stated it was not clear. In the current study the aim is to show that using an algorithm based on the trans-impedance matrix a positive predictive value of twice that observed by Dirr et al. can be achieved, thus the aim is a positive predictive value of 60%.

Following the initial analysis as outlined in this investigation plan, future candidate algorithms developed for the purpose of detecting anomalous electrode position will be evaluated using the data as collected within the current investigation.

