## 5 Justification for the design of the clinical investigation

Several researchers have demonstrated the utility of trans-impedance matrix and other voltage measurements (Hey et al. 2015, Vanpoucke et al. 2004, Vanpoucke et al. 2012) to identify the intra-cochlear electrode positioning. The current investigation is designed to both evaluate a candidate algorithm for detecting the occurrence of gross anomalies in position (e.g. tip fold-over or the electrode array not in the cochlea) and to provide a robust dataset in a clinically representative sample of cochlear implant recipients that can be used to test the specificity and sensitivity of future electrode position feedback algorithms. Such algorithms have potential clinical application in providing objective feedback to the surgeon at the time of electrode insertion to inform the surgeon on electrode placement without additional radiological imaging, and may in future lead to improved clinical outcomes for cochlear implant recipients.

No large database of combined high quality imaging of the intra-cochlear electrode position and reliable trans-impedance measurements exist. It is only relatively recently that it has become possible to determine accurate intra-cochlear electrode position, as a result of advances in scanner technology. Also, the trans-impedance measurements (contained in Custom Sound™ Electro Physiology) that will be used in the study only recently became available. Earlier versions of this tool did not provide sufficient resolution to accurately measure the electrical spread curves.

To explore the decision algorithm, a large dataset is needed. This study will systematically collect a large pool of trans-impedance measurements of CI recipients combined with state of the art imaging of the implanted electrode as part of the clinical routine. Image analysis will allow an expert radiologist/ENT surgeon to determine for each implantation whether it is a normal case or not. The trans-impedance measurements will be analysed by the decision algorithm, and the agreement with the human experts will be established. This exploration of the specificity of the candidate algorithm is the main target of this study, thus being evaluated on the bench without patient involvement.

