2.1 Overview

A total of 154 patients will be assessed in the statistical analysis of the data. This will serve to collect a representative sample of the variability of surgical techniques across clinics and surgeons. The confidence interval to be used in the analyses will be a 90% two-tailed. This confidence interval was deemed to be satisfactory due to the exploratory nature of the study. The statistical analyses conducted for the primary and secondary objectives will lead to the endpoints of the study.

The statistical analysis will be conducted by [REDACTED], Cochlear).

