2.2 Sample size calculation

The goal of the candidate algorithm is to indicate to surgeons and medical staff whether an electrode tip fold-over or electrode outside cochlea appears to have occurred, which should be confirmed radiographically. A target specificity of 98% and confidence level of 90% have been selected.

The 98% specificity target initialises the calculation of the required sample size (N). Since the specificity of the algorithms can only be estimated from a sample population, there is required to be a reasonable expectation that the specificity estimate is equal to or greater than the specificity target. To ensure that the reasonable expectation is fulfilled, the 98% specificity target is set to be the lower bound of the 90% binomial confidence interval for an estimated or measured specificity of 100%. The selected sample size must fulfil this requirement. The binomial confidence interval will be calculated using the Clopper-Pearson exact method and is denoted by Equation 1 and Equation 2:

$$P_{LB} = p : \sum_{i=0}^x \binom{n}{i} p^i (1-p)^{n-i} \approx \frac{\alpha}{2}, \quad \text{for } 0 \leq p \leq P \quad (1)$$

$$P_{UB} = p : \sum_{i=x}^n \binom{n}{i} p^i (1-p)^{n-i} \approx \frac{\alpha}{2}, \quad \text{for } P \leq p \leq 1 \quad (2)$$

where P_{LB} is the lower bound of the binomial confidence interval, P_{UB} is the upper bound of the binomial confidence interval, P is the measured probability of success, p is the probability of success, n is the number of trials, i is the number of successes, x is the measured number of successes and $\alpha = 0.1$ is the level of significance for the 90% confidence interval.

In the Clopper-Pearson method, n is the unknown input in the equation. To find n requires taking into account that there may be occurrences of electrode anomalies in the sample. The range of the possible numbers of anomalies must be estimated such that there is an expected sufficient number of samples (n) to estimate specificity. The sufficient number of samples is calculated by Equation 3 and Equation 4:

$$n = N - m \quad (3)$$

$$m = i : \sum_{i=0}^N \binom{N}{i} p^i (1-p)^{N-i} \approx 0.90, \quad \text{for } 0 \leq i \leq N \quad (4)$$

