where n is the number of sufficient samples required to estimate specificity, N is the total sample size or number of patients required, i is the number of anomalies and p is the probability of an anomaly. We assume that the most prevalent anomaly condition will be a tip foldover. For p we use an estimate of 0.04139 or 4.14% which is based on the perimodiolar weighted average percentage between Grolman et al. (2009) and Zuniga et al. (2017). m is then approximately an upper bound on the number of expected tip fold-overs based on the 90th percentile of the cumulative binomial distribution. In other words, there is at least an approximate 90% chance that there will be m number of tip fold-overs or less.

Determining the sample size N is an iterative process. N is increased from 0 and for each value of N , n is calculated using Equations 3 and 4 which allows for P_{LB} to be calculated using Equation 1. Once P_{LB} is approximately 0.98 or 98%, the corresponding N is selected as the sample size.

Using the denoted method (see Appendix A) a sample size of $N = 154$ was selected which had a 89% chance of 9 or less tip fold-overs taking place, resulting in an $m = 9$ and $n = 145$. With a measured specificity (i.e. estimated specificity) of 100% and $n = 145$, the $P_{LB} = 0.9797$ which is approximately 98%.

With an algorithm target specificity of at least 98%, a target sensitivity of at least 90%, an estimated probability of a tip fold-over of 4.14%, the positive predictive value (PPV) is equal to 66.02%. This entails that after the algorithm has detected a tip fold-over, it is estimated that two thirds subset of patients will be confirmed by imaging to have a tip fold-over. The calculation of PPV is calculated by Equation 5:

$$PPV = \frac{(prevalence * sensitivity)}{(prevalence * sensitivity) + ((1 - prevalence) \times (1 - specificity))} \quad (5)$$

$$PPV = \frac{(0.0414 * 0.90)}{(0.0414 * 0.90) + ((1 - 0.0414) \times (1 - 0.98))} = 0.6602 \quad (6)$$

where in this application *prevalence* is the estimated rate of tip fold-overs.

3 Conduction of statistical analysis

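### The specificity set drops anomaly types that the algorithm is not meant to flag, but the PPV applies that specificity to them

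*Protocol*

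**What the plan says.** **Target.** Protocol 3 says the algorithm "indicates whether a tip fold-over or array outside the cochlea have been detected". SAP 3.1 defines the output in the same way: 0 means neither of these two conditions, 1 means one of them.

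**Exclusion.** Protocol 9.3 lists tip fold-over, scala displacement, extrusion or shallow insertion, and over-insertion as insertion-related events. It then says that "insertions that have insertion related events or a poor medial lateral should be excluded from the dataset". No cut-off for a poor medial-lateral position is given. Protocol 8.1 adds: "Those insertions showing the presence of anomalous properties will be excluded from the dataset that is presented to the candidate algorithm". Protocol 9.2 and SAP 6 restrict the analysis in the same direction.

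**Negative case.** Protocol 3 defines a negative as a successful insertion whose position is not anomalous, with no reference to the two targets. Protocol 2 defines specificity among insertions that CT/DVT has verified as normal.

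**Use of the result.** SAP 2.2 computes a PPV of 66.02% with prevalence equal to the tip fold-over rate alone. Protocol 9.1 uses this calculation to say that the 60% PPV aim of Protocol 3 is met.

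**Which insertions are run.** Protocol 8.1 first says that the 154 classified insertions go to the algorithm, and later in the same section removes the anomalous ones. SAP 3.1 step 1 runs it on each patient's data, with a sub-item naming normal insertions, and places radiographic classification after the run, at step 4.

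**The concern.** Take an over-inserted array that is inside the cochlea and not folded. Under the output definition in SAP 3.1 the correct answer is 0, so an alarm is a false positive. Under the exclusion in Protocol 9.3 the case does not enter the specificity analysis. In the PPV formula the same case sits in the (1 − prevalence) term and is credited with 98% specificity. The group in which specificity is measured and the group to which it is applied therefore differ.

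The intended use makes this matter. Protocol 3 looks ahead to feedback during or just after insertion, and Protocol 8.2 allows the post-insertion CT to follow surgery. A user in theatre could not first remove insertions that CT would later call displaced or too deep. What is at stake is the PPV claim and any statement about false alarms in unselected insertions. The clean-insertion specificity is not in doubt.

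**Working it through.** **Inputs from the documents**
- Interval: "The confidence interval to be used in the analyses will be a 90% two-tailed" (SAP 2.1).
- Target: "A target specificity of 98% and confidence level of 90% have been selected" (SAP 2.2).
- Tip fold-over rate: "For p we use an estimate of 0.04139 or 4.14" per cent (SAP 2.2).
- Assumed sensitivity: 90% (Protocol 9.2 footnote, SAP 2.2).
- Total N = 154, allowance of 9 fold-overs, n = 145 (Protocol 9.1, SAP 2.2).

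**The plan's own figures**
- Fold-over rate: (5 + 4)/(0.48 × 303 + 72) = 9/217.44 = 0.04139.
- P(X ≤ 9 | 154, 0.04139) = 0.892, the stated 89%; n = 154 − 9 = 145.
- Exact lower bound at 145/145: 0.05^(1/145) = 97.96%. The stated 97.97% is slightly higher because the Appendix A grid search accepts tail probabilities up to 0.052.
- PPV = 0.04139 × 0.90 / (0.04139 × 0.90 + 0.95861 × 0.02) = 66.02%, as stated.

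The figures reproduce. The allowance of 9 is sized on tip fold-over alone.

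**Inputs the documents do not give (assumed)**
- q, the share of all insertions with a non-target anomaly. Protocol 3 says only that suboptimal positions overall occur in a few per cent. Range shown: 2% to 20%.
- f2, the false-alarm rate in that group. No source. Range shown: 2% to 20%.
- f1, the false-alarm rate in clean insertions, set at the design limit of 2%.

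**False-positive rate over all insertions without a fold-over**

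FPR = [(0.9586 − q) × f1 + q × f2] / 0.9586, then the SAP's PPV formula. As in the SAP, arrays outside the cochlea are given no separate rate.

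Example, q = 5% and f2 = 10%: FPR = (0.9086 × 0.02 + 0.05 × 0.10)/0.9586 = 0.023172/0.9586 = 2.42%. PPV = 0.03726/(0.03726 + 0.023172) = 61.7%.

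| q | f2 | FPR | PPV |
|---|---|---|---|
| any | 2% (= f1) | 2.00% | 66.0% |
| 2% | 10% | 2.17% | 64.2% |
| 2% | 20% | 2.38% | 62.1% |
| 5% | 10% | 2.42% | 61.7% |
| 5% | 20% | 2.94% | 56.9% |
| 10% | 10% | 2.83% | 57.8% |
| 10% | 20% | 3.88% | 50.1% |
| 20% | 20% | 5.76% | 40.3% |

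The direction is not fixed. With q = 5% and f2 = 0, FPR = 0.018172/0.9586 = 1.90% and PPV = 0.03726/(0.03726 + 0.018172) = 67.2%.

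**Break-even for a PPV of 60%**

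Largest FPR = 0.0414 × 0.9 × (1/0.6 − 1)/0.9586 = 0.02484/0.9586 = 2.59%.

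Required f2 = [0.02484 − (0.9586 − q) × 0.02]/q:
- q = 2%: 0.006068/0.02 = 30%
- q = 5%: 0.006668/0.05 = 13%
- q = 10%: 0.007668/0.10 = 7.7%
- q = 20%: 0.009668/0.20 = 4.8%

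If clean insertions give only 1% false alarms, q = 5% needs (0.02484 − 0.9086 × 0.01)/0.05 = 32%.

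**The case against.** The strongest reply is that the exclusion follows the protocol's own definition. A negative is any non-anomalous position, and Protocol 3 lists too shallow, too deep and lateral placements as positions the surgeon should have the chance to correct. On that view an alarm on such an array is not plainly false. This stands as far as it goes, but the output definition in SAP 3.1 and the PPV formula in SAP 2.2 use the narrower target. The plan cannot use one meaning to measure specificity and the other to apply it.

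Several stronger readings are tempting, and the documents do not support them:
- A reader might infer that false alarms in practice are likely understated, because badly placed arrays are the hardest negatives. Protocol 3 says only that the matrix can be related to some aspects of position. Nothing shows that over-insertion or scala displacement looks like a fold-over to this algorithm.
- A reader might take the one-in-fifty statement in Protocol 9.1 as a claim about all patients. It is already limited to insertions in normal position.
- A reader might see a conflict with the aim in Protocol 5 of a "robust dataset in a clinically representative sample of cochlear implant recipients". That phrase describes the dataset for testing future algorithms, and the database keeps the anomalous insertions.
- A reader might conclude that the algorithm is certain never to see these cases. Protocol 8.1 and SAP 3.1 are inconsistent on this.

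It is also fair that an added analysis would be small. A share of 2% to 5% of 154 is about 3 to 8 cases, and no alarms in 5 cases leaves a one-sided 95% upper limit of 1 − 0.05^(1/5) = 45%. That limits what counts by anomaly type can show. It does not justify crediting those cases with 98% specificity.

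**Conclusion.** The point holds as a mismatch between where specificity is measured and where it is applied. The exclusion is wider than the algorithm's two targets, and the 66.02% PPV rests on a specificity that the planned analysis does not test in the excluded types. The bias is possible but not shown, and its size and direction are unknown.

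If suboptimal positions really total a few per cent, the effect is modest: at q of 2% to 5% and f2 of 10% to 20%, PPV runs from 64.2% down to 56.9%, around the 60% aim. The larger losses need shares of 10% to 20%, which are unlikely unless the undefined medial-lateral rule removes many cases. All of these results take 2% false alarms in clean insertions, the design limit; a lower rate leaves more room. The clean-insertion specificity remains valid for what it measures.

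**What to change.** 1. Reconcile the definition of a negative case (Protocol 3) with the exclusion (Protocol 8.1, 9.2, 9.3; SAP 6), the output definition and run steps (SAP 3.1) and the PPV formula (SAP 2.2). State whether all 154 insertions are run. Give the medial-lateral cut-off, and say whether extrusion and shallow insertion count as an array outside the cochlea.
2. Keep specificity in clean insertions as the primary analysis, and label it as such.
3. Run the same locked algorithm on every insertion that has a recording. As a secondary result, report specificity among all insertions without a fold-over and inside the cochlea, with its exact interval, plus descriptive alarm counts by anomaly type.
4. Compute PPV from that secondary specificity. Otherwise state that the 98% and PPV figures apply only to insertions free of any anomaly.

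The cost is a change of wording and one more bench run on stored data, with no extra patients or procedures. The downside is that the secondary specificity and PPV may be less favourable: with 145 cases, a single alarm lowers the exact bound from 97.96% to 96.77%. It should therefore be read as an estimate, not as a second test against 98%. Counts by anomaly type will be small and descriptive only.
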